2.2.6 Rationale for stability of virologic and immunologic measurements while on suppressive ART

HIV-specific CD8+ cells frequently decline after initiation of ART [57] but recent unpublished data from ACTG 5281 suggest that these T-cell frequencies stabilize on suppressive ART and demonstrate little change over 14 weeks of observation [[name], personal communication]. Furthermore, no significant changes in the levels of cell-associated RNA in patients on suppressive ART have been observed when measured at intervals 2 weeks to 2 months apart [[name], personal communication]. Although the prevalence of detectable low level residual plasma viremia varies between studies incorporating the use of the single-copy RNA assay, stability of residual viremia on suppressive ART has been demonstrated in several studies [58]. These findings support the assumption that there would be no change or zero mean change in these measurements in a placebo arm if one were to be incorporated.

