9.6.1 Primary Analyses

For the primary safety analysis, \geq Grade 3 AEs attributed to study treatment and confirmed CD4+ declines (see section 9.2.1.1) will be summarized. In addition, all other reported AEs \leq Grade 2 attributed to study treatment as well as all reported events \geq Grade 2 (regardless of treatment relatedness) will be summarized. All **participants** who have been exposed to study treatment will be included in the analysis.

For the primary immunologic (see section 9.2.1.2) and virologic (see section 9.2.1.3) efficacy outcomes, post-treatment changes will be evaluated comparing measurements pre-treatment (averaged) to the measurement 20 weeks after starting study treatment, testing the null hypothesis of no difference pre-treatment versus post-treatment using a paired t-test. Log-transformations may be applied for the virologic outcomes. To address anticipated left-censoring of SCA measurements, a value one half the lower assay limit will be imputed. If feasible with the modest sample size, censored-data longitudinal data methods that statistically address the

issue of left-censoring (SCA measurements below assay limits) will also be used to evaluate and estimate treatment effects [59]. Mean and quartile plots will summarize the immunologic and virologic measurements at each visit. Because the aim of this pilot study is to investigate the biologic effects of sirolimus, the analyses will be as-treated, limited to **participants** who have data at baseline and week 32 (20 weeks on sirolimus) and who remained on study treatment and ART (and without virologic failure) through week 32. A supplemental analysis will be based on changes from baseline to the last available time point for a **participant** while on study treatment and ART (and without virologic failure).

If there is evidence that there is a significant difference between the week 0 and week 12 levels of the primary immunologic and virologic efficacy measurements, based on paired t-tests between these two time points, then the primary analysis will instead be based on a comparison of slopes pre- versus post-treatment (see 9.6.2). Both sets of results, from the paired t-test analyses and the comparison of slopes analyses, will be reported in the presentation of the study findings.

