9.6.2 Secondary Analyses

Additional analyses of safety will summarize the magnitude of CD4+ cell changes baseline to post-treatment time points (mean, quartiles). Analyses will also summarize the number of **participants** who exhibit on two consecutive measurements HIV RNA >200 copies/mL on conventional assay. Tolerability will be assessed by the number of **participants** who prematurely discontinue study treatment and the reasons for discontinuation.

Analyses of secondary virologic and immunologic outcomes will parallel the primary analyses outlined in section 9.6.1. Graphical approaches will summarize the virologic and immunologic measurements over time. Supplemental analyses will compare the change in the slope-over-time pre-treatment (pre-entry to start of treatment) versus post-treatment (start of treatment through week 20 while on treatment) and also may examine the change from baseline to the average of the week 16, 24 and 32 (4, 12, 20 weeks on sirolimus) measurements. Soluble markers (e.g., IL-6 levels) will be log-transformed.

Analyses will also summarize changes in immunologic and virologic measures after discontinuation of study treatment.

Associations between changes in the various immunologic and virologic measurements will be evaluated using scatterplots and correlations coefficients.

The relationship between anal HPV, particularly HPV 16, and immunological measurements of activation and virological measurements of HIV reservoir size will be correlated.

The effect of study treatment on anal dysplasia will be described by evaluating the change in anal Pap tests after study therapy. Pap tests will be categorized as

normal or abnormal according to standard clinical criteria.

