5.3 Visit Schedule and Definition of Week for Analysis Purposes

The visit schedule for key study outcomes is shown in Table 1.

The protocol requires evaluations to be scheduled at the **treatment week 0** visit, ± 1 day at the **treatment week 1, 2 and 4** visits, ± 1 week at the **treatment week 8, 12 and 20** visits, and ± 2 weeks at the **treatment week 32*** visit. The analysis window for post-entry visits will be calculated based on the number of **weeks** since the initial dose of sirolimus and broader windows will be used (as compared to the protocol specified window) in order to minimize the impact of deviations from the desired schedule. If there are multiple evaluations within the window for a given visit, then the evaluation closest to the scheduled study week will be used (and the later measurement will be used if there are two measurements which are equally distant from the scheduled week). Table 1 **below** details the **analysis windows for clinical data**.

For the primary and secondary outcome measures, and the exploratory soluble marker outcome, a database review was conducted by the study chair to identify the time points to be tested based on the availability of samples and the duration of sirolimus use. This resulted in a total of 159 time points for 29 study participants.

- For 16 participants with the full 20 weeks of sirolimus use who will constitute the primary efficacy population: treatment weeks -12, 0, 4, 12, 20 and 32*
- For the 13 participants with at least 6 but less than 20 weeks of sirolimus use: treatment weeks -12, 0, 4, 12 and 20*

Note: One participant went off study early and only has weeks -12, 0 and 4.

Note: Treatment weeks 32* and 20* refer to time points after sirolimus discontinuation. Data from these time points will be used to assess durability of treatment effects and will not be included in the as-treated analysis of efficacy.

Table 1: Study Visit Schedule and Analysis Windows

Evaluation	Screening	Entry	Sirolimus Initiation	Post-Entry Evaluations						
	Treatment Week	-12	0	1	2	4	8	12	20	32
Analysis Window (Weeks Post-Sirolimus Initiation)		0	(0 – 1]	(1 – 3]	(3 – 6]	(6 – 10]	(10 – 16]	(16 – 26]	(26 – 37]	
Clinical Assessment	X	X	X	X	X	X	X	X	X	X
Hematology	X	X	X	X	X	X	X	X	X	X
Liver Function Tests	X	X	X	X	X	X	X	X	X	X
Blood Chemistry	X	X	X	X	X	X	X	X	X	X
Calculated Creatinine Clearance	X	X	X	X	X	X	X	X	X	X
Urinalysis	X		X			X	X	X		
CD4+/CD8+	X	X	X		X	X	X	X	X	X
Plasma HIV-1 RNA	X	X	X			X	X	X	X	X

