If there is evidence that there is a significant **effect of sirolimus on a primary immunologic or virologic efficacy outcome and also a significant** difference between the week 0 and week 12 (**treatment weeks -12 and 0**) levels of the measurements, based on paired t-tests between these two time points, then **additional analyses and summaries will be performed. In particular**, the primary analysis will be supplemented with an analysis based on a comparison of slopes pre- versus post-treatment. Both sets of results, from the paired t-test analyses and the comparison of slopes analyses, will be reported.

For the primary efficacy analysis population, a summary/listing of gaps or holds in sirolimus or ART use from entry through treatment week 32*.

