14 SECONDARY OUTCOME MEASURES

ANALYSES:

Additional analyses of safety will summarize the magnitude of CD4+ T-cell changes baseline to post-treatment time points (means over time, participant-specific curves). Analyses will also summarize the number of **participants** who exhibit on two consecutive measurements HIV RNA >200 copies/mL on conventional assay. Tolerability will be assessed by the number of **participants** who prematurely discontinue study treatment and the reasons for discontinuation. **The analysis population for these CD4, HIV-RNA, and tolerability assessments will be the safety population.**

Analyses of secondary virologic and immunologic outcomes will parallel the primary analysis. **The secondary efficacy analysis population is defined as participants who completed at least 6 weeks of sirolimus.** Paired t-tests will compare measurements pre-treatment (averaged) to the measurement at treatment week 20 for the primary efficacy population and treatment week 4 for the secondary efficacy population. Graphical approaches will summarize the virologic and immunologic measurements over time, **through treatment week 32 for the primary efficacy population and, separately, through treatment week 4 for the secondary efficacy population.** Soluble markers (eg, IL-6 levels) will be log10-transformed.

Analyses will also summarize changes in immunologic and virologic measures after discontinuation of study treatment. **Paired t-tests will compare the measurements at treatment week 20 to treatment week 32* for the primary efficacy analysis population.**

For the primary analysis population, trough sirolimus levels (during the 20 weeks of treatment) will be summarized by descriptive statistics on the participant-specific average of all available sirolimus levels (minimum, 10th, 25th, median, 75th, 90th, maximum). In addition, the number of trough levels per participant will be summarized. To provide information regarding pharmacodynamics, scatterplots and correlations

will assess the relationship between average trough level and change from baseline to week 20 outcomes. These correlations will be restricted to outcomes with evidence of change following sirolimus treatment.

Associations between changes in the various immunologic and virologic measurements will be evaluated using scatterplots and correlations coefficients.

OUTCOMES:

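### Protocol and SAP disagree on which analysis is primary if the lead-in shows a change, and the SAP runs its slope check only when two tests are both significant

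*SAP*

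**What the plan says.** Both documents define baseline as the mean of the entry and week 12 values (treatment weeks -12 and 0) and compare it with treatment week 20 by a paired t-test.

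- **Protocol 9.6.1.** If weeks 0 and 12 differ significantly, "then the primary analysis will instead be based on a comparison of slopes pre- versus post-treatment". Both sets of results are reported.
- **SAP 13.2.** The trigger is a significant "effect of sirolimus on a primary immunologic or virologic efficacy outcome and also a significant" difference between the two lead-in visits. The consequence is that "the primary analysis will be supplemented with an analysis based on a comparison of slopes pre- versus post-treatment". SAP section 2 logs an updated approach to baseline differences under Version 4.0, without a reason and without saying that protocol 9.6.1 is superseded.
- **Protocol 9.6.2.** With no significance condition: "Supplemental analyses will compare the change in the slope-over-time pre-treatment" with that on treatment. SAP section 14 does not carry this over, so the gated rule in 13.2 is the SAP's only slope analysis.
- **Samples (SAP 5.3).** "This resulted in a total of 159 time points for 29 study participants", and "One participant went off study early and only has weeks -12, 0 and 4".
- **Other evidence on drift.** SAP 13.2 plans plots at each visit. SAP section 14 adds a week 4 test, and "Paired t-tests will compare the measurements at treatment week 20 to treatment week" 32*, which is after sirolimus has stopped.
- **Stability evidence (Protocol 2.2.6).** HIV-specific CD8 frequencies "demonstrate little change over 14 weeks of observation". The intervals for cell-associated RNA run from 2 weeks to 2 months. No interval is given for the single-copy assay (SCA).

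**The concern.** There is no control arm, so attributing a change to sirolimus rests on the assumption that nothing would have changed without it. The lead-in is the trial's own evidence for that assumption.

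If only the lead-in test is significant, the protocol makes slopes primary and the SAP requires no slope analysis. If both tests are significant, both documents report both analyses but disagree on which is primary.

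Each rule also has its own defect:

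- The SAP's gate looks for drift with a weak test, and only after a positive result. A natural trend can pass as a drug effect, and a drug effect hidden by drift never opens the gate.
- The protocol's switch chooses the slope test because the entry and week 12 values happened to differ, then uses the same values in the slope test.

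The SAP also does not say whether the lead-in test uses the 16 participants in the primary efficacy population or all 29 with both lead-in samples.

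**Working it through.** **Plan's own figure.** Protocol 9.4 states 80% power for 0.59 SD with n = 25 and two-sided alpha 0.05. The noncentral t with noncentrality 0.59 × √25 = 2.95 gives 80.8%, so the figure reproduces. At the 16 anticipated in SAP 13.2, power for 0.59 SD is 59.8% and the effect detectable with 80% power is 0.75 SD.

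**Samples.** 16 × 6 + 12 × 5 + 1 × 3 = 96 + 60 + 3 = 159, which matches SAP 5.3. All 29 therefore have both lead-in time points selected.

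**Assumptions, not in the documents.** Normal errors with correlation ρ^(weeks/12), ρ = 0, 0.5 or 0.8; the same linear drift in every participant; no censoring; 0.05 two-sided for the lead-in test.

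**Why the lead-in test is weak.** Baseline is centred at week (-12 + 0)/2 = -6, so the primary contrast carries 20 - (-6) = 26 weeks of drift. The lead-in contrast carries 12. With error SD σ, the primary change has SD 1.225 / 1.130 / 0.812 σ and the lead-in change 1.414 / 1.000 / 0.632 σ. Drift that looks like d SD in the primary contrast has a standardised size in the lead-in of

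d × (12/26) × SD(primary) / SD(lead-in).

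For d = 0.75 and ρ = 0 this is 0.75 × 0.4615 × 1.225/1.414 = 0.30, for which a t-test on 16 has 20% power.

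**Pure drift, no drug effect** (simulation, 60,000 trials):

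| Case | Primary rejects | Lead-in flags, ρ = 0 / 0.5 / 0.8 | False positive with no flag |
|---|---|---|---|
| 0.75 SD, lead-in test on 16 | 80% | 20 / 31 / 38% | 64 / 54 / 47% |
| 0.59 SD, lead-in test on 16 | 60% | 14 / 21 / 26% | 51 / 46 / 42% |
| 0.75 SD, lead-in test on 29 | 80% | 35 / 53 / 64% | 52 / 37 / 27% |

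At ρ = 0 the two contrasts are uncorrelated, so the first row can be checked by hand: 0.80 × (1 - 0.20) = 0.64.

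**What the lead-in can exclude.** The 95% CI half-width projected to 26 weeks, in SDs of the primary change, is t × SD(lead-in)/√n × (26/12) / SD(primary). For n = 16 and ρ = 0 this is 2.131 × 1.414/4 × 2.167/1.225 = 1.33. The three values are 1.33 / 1.02 / 0.90 at n = 16 and 0.95 / 0.73 / 0.64 at n = 29, against a detectable effect of 0.75.

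**Real 0.75 SD effect cancelled by drift.** The SAP's check needs both tests significant. At ρ = 0 that is about 0.20 × 0.05 = 1.0%; the simulated values are 1.0 / 1.6 / 2.2%.

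**Protocol switch, no drift and no effect** (200,000 trials). The slope test is each participant's least-squares slope over treatment weeks 0, 4, 12 and 20, minus (week 0 - week -12)/12. It rejects in 63 / 51 / 44% of switched trials. At ρ = 0, overall type I error is about 0.95 × 0.05 + 0.05 × 0.63 = 0.079. Simulated: 7.9 / 7.2 / 6.8% at n = 16 and 8.0 / 7.4 / 6.8% at n = 25. If the on-treatment slope starts at week 4, it is 6.6–6.9% (n = 16).

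**Slope test run without a gate.** It rejects in about 5% of trials with or without linear drift.

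**The case against.** **Disclosure.** The SAP change is logged and bolded, and the SAP allows the team to modify the plan. That stands, but the log entry gives no reason and does not say which document governs.

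**The two harms belong to different rules.** Type I inflation arises only under the protocol's switch, and undetected drift without a slope check is mainly the SAP's problem. That is correct. They are not additive; each is a reason not to settle the conflict by adopting that rule as it stands.

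**An ungated slope comparison is already planned in protocol 9.6.2.** True, but the SAP omits it, and the SAP describes itself as the core of any publication.

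**Other safeguards exist.** The visit plots are unconditional. If the effect is gone by week 32*, the week 20 versus 32* test would reject in 94–100% of the cancelled-effect trials, and a reversal argues against continuing drift. This is real help, but it depends on the effect washing out within 12 weeks and it sits under secondary outcomes.

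**The lead-in population is implied.** The rule's place in SAP 13.2 does point to the 16, so this is a minor ambiguity.

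**The drift is hypothetical and censoring is ignored.** No document suggests drift of this size. For SCA, with half-limit imputation and an assumed limit at the baseline median, the flags for the 0.75 SD case fall to about 15–25% and the ungated slope test rejects in about 5–7%. Censoring therefore weakens the gate further, and the slope test's 5% level is only approximate for SCA.

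**The slope contrast has little power.** This stands and limits it to a supporting role.

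**Conclusion.** The concern holds. The conflict is in current text and depends on no assumption: the trigger and the consequence both differ, and the documents do not settle which analysis is primary when the lead-in changes.

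The sizes are illustrative, because drift and correlation are assumed. At n = 16, drift able to produce an 80% false-positive rate would pass without the SAP's slope check in 47–64% of all trials. The SAP's check would run in about 1–2% of trials where drift cancels a 0.75 SD effect. The protocol's switch gives type I error of about 6.6–8.0%.

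The paired t-test itself remains valid if the outcomes are stable without sirolimus. This should be fixed, but it does not invalidate the trial.

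**What to change.** Name the paired t-test as the single primary analysis in both documents. Delete the protocol's switch and the SAP's double-significance condition. Suggested SAP text:

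> For each primary efficacy outcome, whatever the result of the primary test, we will report with 95% CI (a) the mean change from treatment week -12 to 0, in the primary efficacy population and in all participants with both samples (planned n = 29), and (b) the on-treatment slope (treatment weeks 0 to 20) minus the lead-in slope, as a supporting estimate with low power.

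Item (b) restores the comparison in protocol 9.6.2. If the protocol is not to be amended again, the SAP should state that this text supersedes the switch in 9.6.1 and give the reason.

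The cost is wording and two estimates per outcome, on samples already selected. A protocol amendment would also need ethics approval and registration (protocol 4.3.1). The limits should be stated with the results:

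- At n = 16 the slope contrast has only 10–17% power for a 0.59 SD step, or 14–25% if the effect builds linearly to week 20, and it assumes linear drift.
- The 29-person estimate assumes that the 13 who stopped sirolimus early drift like the other 16. Reporting both sets shows whether they differ.

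### SAP 13.2 triggers the slope comparison on the same lead-in difference that forms its pre-treatment slope, so its p-value is not valid once triggered, and the trigger misses most drift-driven results

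*SAP*

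**What the plan says.** SAP 13.2 keeps the paired t-test (average of entry and week 12 against treatment week 20) as the primary efficacy analysis. A slope comparison is added only if two conditions hold. There must be a significant "effect of sirolimus on a primary immunologic or virologic efficacy outcome and also a significant" difference between treatment weeks -12 and 0 in the "levels of the measurements, based on paired t-tests between these two time points". In that case "the primary analysis will be supplemented with an analysis based on a comparison of slopes pre- versus post-treatment", and "Both sets of results, from the paired t-test analyses and the comparison of slopes analyses, will be reported".

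Protocol 9.6.1 has a different rule. A significant lead-in difference alone is enough, "then the primary analysis will instead be based on a comparison of slopes pre- versus post-treatment".

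Only Protocol 9.6.2 defines the slopes: "Supplemental analyses will compare the change in the slope-over-time pre-treatment (pre-entry to start of treatment) versus post-treatment", the latter running from the start of treatment through week 20 on treatment. SAP 5.3 lists the samples for the primary efficacy population as "treatment weeks -12, 0, 4, 12, 20 and 32", the last being after sirolimus has stopped. That leaves two samples before sirolimus and three on it. Neither document gives a slope model, an allowance for selection by the trigger, or a rule for reading discordant results.

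**The concern.** A line through two points has no information beyond their difference. The pre-treatment slope is therefore the triggering difference divided by 12, and the slope test is run only in data sets where one component of its own statistic is already extreme. If the post-treatment slope starts at treatment week 0, as Protocol 9.6.2 implies, that value also enters both slopes with opposite effect.

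This is a single-arm trial, and the lead-in is its only internal evidence on drift. A test selected in this way can appear to confirm or contradict a positive primary result largely according to chance variation in the lead-in. Gating it on significance also means that the drift evidence is examined formally only when a small lead-in comparison happens to reach significance.

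**Working it through.** **Inputs.** n=16 (SAP 13.2); n=25, 0.59 SD of change, two-sided alpha 0.05 and 80% power (Protocol 9.4); baseline as the mean of weeks -12 and 0 (SAP 5.1); sample times -12, 0, 4, 12 and 20 (SAP 5.3).

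**Assumptions not in the documents.** Normal errors with equal variance (error SD = 1), independent given the participant's mean; both triggers at two-sided 5%; slope test as a one-sample t-test on each participant's least-squares post slope minus pre slope. Sensitivity cases: serial correlation of 0.5 per 12 weeks; random slopes with SD 0.5 error SD per 12 weeks; post slope without week 0.

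**1. The plan's own figure.** The noncentral t gives 80.8% power at n=25 and 0.59 SD, matching the stated 80%. At n=16 it gives 59.8%.

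**2. Link between trigger and slope contrast.**
- Var(pre slope) = 2/144 = 0.01389.
- Post slope on 0, 4, 12, 20 (mean 9, sum of squares 81+25+9+121 = 236): variance 1/236 = 0.00424.
- Covariance through week 0 = (1/12) x (-9/236) = -0.00318.
- Var(post minus pre) = 0.01389 + 0.00424 + 2 x 0.00318 = 0.02448, so SD = 0.1565.
- Correlation with the lead-in difference = (-0.00318 - 0.01389)/sqrt(0.02448 x 0.01389) = -0.93.
- Without week 0 in the post slope, the variance is 1/128 = 0.00781 and the covariance is 0. The correlation is then -sqrt(0.01389/0.02170) = -0.80.

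**3. Rejection after triggering, no effect and no drift (simulation, n=16).**

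| Trigger | Independent errors | Correlated errors or random slopes |
|---|---|---|
| SAP, both conditions | about 55% (45% without week 0 in the post slope) | about 17-27% |
| Protocol 9.6.1, lead-in only | about 62% (42% without week 0) | about 51-52% with week 0 |

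Without a trigger, the slope test rejects in 5%, so the selection causes the excess. Under the Protocol 9.6.1 switch the two-stage error is about 7-8%. Under the SAP the dual trigger fires in about 0.3% of null outcomes. With independent errors the figure is 0.25%, so a trigger followed by slope rejection occurs in about 0.0025 x 0.55 = 0.14% per outcome.

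**4. A real effect of 0.59 SD, no drift.** The paired change has variance 1 + 1/2 = 1.5, so the effect is 0.59 x 1.225 = 0.723 error SD.
- Gradual effect: contrast 0.723/20 = 0.0361 per week; 0.0361/0.1565 x sqrt(16) = 0.92, power 14%.
- Step effect: contrast 0.723 x 9/236 = 0.0276; noncentrality 0.70, power 10%.
- Without week 0 in the post slope: 5% (step) and 15% (gradual).
- Random slopes, gradual effect, without week 0: change variance 1.5 + (0.5 x 26/12)^2 = 2.67; effect 0.59 x 1.635 = 0.965; noncentrality (0.965/20)/0.1473 x 4 = 1.31, power about 23%.

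The range is therefore about 5-23%, against 60% for the paired test. The dual trigger fires in about 3% of such outcomes. With independent errors and week 0 in the post slope, the slope test then confirms the effect in over 99% of cases if the chance lead-in difference runs opposite to it. If it runs the same way, the test confirms in none, and the slope estimate has the wrong sign in 97-99%. Without week 0 in the post slope the figures are 53-94% and 0%, with the wrong sign in 80-99%.

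**5. A continuing drift of 0.5 error SD per 12 weeks, no drug effect, independent errors.**
- Paired test: 26 weeks separate the mean baseline time (-6) from week 20. The shift is 0.5 x 26/12 = 1.083; 1.083/1.225 = 0.885 SD, so it rejects in 91%.
- Lead-in test: 0.5/1.414 = 0.354 SD, significant in 26%.
- Both together: 24%. The trigger therefore opens in 24/91, or about 26%, of the trials with a drift-driven paired result.
- Slope test: rejects in 5% overall and about 8% of dual-triggered trials.

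**The case against.** The strongest reply is that the SAP's rule is narrower than the protocol's. It also requires a significant sirolimus effect, leaves the paired t-test primary and reports both results. All of that stands, and it rules out three stronger readings.

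- A reader might infer that the plan inflates its primary type I error to about 8%. That follows only from the Protocol 9.6.1 switch. Under SAP 13.2 the slope test cannot turn a non-significant primary result into a significant one.
- A reader might apply a rejection rate of about 6 in 10 to the SAP. That figure belongs to the lead-in-only trigger with independent errors.
- A reader might conclude that slopes should be dropped in favour of a baseline at treatment week 0 alone. The drift case does not support this: the slope contrast holds its 5% level there. The week-0-only test has shift 0.5 x 20/12 = 0.833; 0.833/1.414 = 0.589 SD, so it rejects in about 60%. At a drift of 1.06 SD per 12 weeks it rejects in nearly all trials. Its power for a real 0.59 SD effect is also lower, about 48%.

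It is also fair that an unconditional power figure does not describe a test run only when triggered. It is given here because it shows what an untriggered slope contrast can deliver.

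The reply does not rescue the triggered p-value. A chance lead-in difference in the same direction as a real effect leads to non-confirmation, and so, usually, does genuine continuing drift. The triggered test cannot tell these apart.

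**Conclusion.** The point holds in a limited form. After triggering, the slope p-value has no 5% meaning: with no effect and no drift it rejects in about 55% of dual-triggered cases with independent errors, and about 17-27% with correlated errors or random slopes. With a real effect and no drift, a triggered result mostly repeats the direction of the lead-in difference. The trigger also leaves about three quarters of drift-driven primary findings without a slope analysis at 0.5 error SD of drift per 12 weeks.

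The consequence is for interpretation, not for error control. In the SAP the analysis is supplementary and seldom triggered by chance (about 0.3% of null outcomes, about 3% with a real 0.59 SD effect), and the primary type I error is unaffected. The algebraic identity between trigger and pre slope needs only the two-sample lead-in. The percentages rest on the normal error models above, on n=16, and on reading the protocol's week 20 as treatment week 20.

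**What to change.** Remove the significance trigger from SAP 13.2 and leave the paired t-test as it is. For every primary outcome, report beside it:

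1. the lead-in change (treatment week 0 minus week -12) with a 95% confidence interval;
2. the post-minus-pre slope contrast as an estimate with a 95% confidence interval, with no claim based on its p-value.

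State the slope model: which time points enter the post slope, whether week 0 is one of them, how participants are weighted, and that week 20 means treatment week 20. State that the Protocol 9.6.1 switch making slopes primary does not apply. A week-0-only baseline may be added as a sensitivity analysis, with a note that it does not protect against continuing drift.

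The cost is wording and one extra table. The intervals will be wide. With independent errors at n=16, the slope contrast has a half-width of 2.131 x 0.1565/4 = 0.083 error SD per week, or about 1.67 over 20 weeks, against an effect of 0.72. The lead-in change has a half-width of 2.131 x 1.414/4 = 0.75 error SD, so it often could not exclude a drift of 0.5. Showing that uncertainty for every outcome is more informative than a test that appears only after selection.
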